4 DETERMINATION OF SAMPLE SIZE

The primary objective of this study is to investigate the tolerability of tazemetostat. Hence neither clinical hypothesis nor judgment criteria are set, the sample size is not based on statistical consideration. The sample size of 6 patients is considered adequate for the purpose to evaluate tolerability of each cohort.

5 STATISTICAL METHODS

All descriptive statistics for continuous variables will be reported using mean, standard deviation, median, minimum and maximum. Categorical variables will be summarized as number (percentage) of subjects.

5.1 Study Endpoints

5.1.1 Primary Endpoint

- DLTs

5.1.2 Secondary Endpoints

- Safety assessments (adverse events (AEs), clinical laboratory tests, vital signs, body weight, 12-lead electrocardiograms (ECGs), echocardiograms/ multigated acquisition (MUGA) scans to assess left ventricular ejection fraction (LVEF), Eastern Cooperative Oncology Group - Performance Status (ECOG-PS), and physical examinations)
- PK parameters
- Objective response rate (ORR) of best overall response (BOR)

5.1.2.1 Pharmacokinetic (PK) Endpoints

PK parameters derived by non-compartmental analysis using plasma concentrations of tazemetostat and ER-897387 which include, but are not limited to, are shown as below:

Cycle 0 Day 1:

- maximum observed concentration (C_{\max})
- time at which the highest drug concentration occurs (t_{\max})
- area under the concentration–time curve from zero time to 12 h ($AUC_{(0-12h)}$)
- area under the concentration–time curve from zero time to time of last quantifiable concentration ($AUC_{(0-t)}$)
- area under the concentration–time curve from zero time extrapolated to infinite time ($AUC_{(0-inf)}$)

- terminal phase rate constant (λ_z)
- terminal elimination phase half-life ($t_{1/2}$)
- apparent total clearance following oral administration (CL/F) (tazemetostat only)
- apparent volume of distribution at terminal phase (V_z/F) (tazemetostat only)
- mean residence time (MRT)

Cycle 1 Day 15:

- area under the concentration–time curve over the dosing interval on multiple dosing ($AUC_{(0-\tau)}$)
- average steady state concentration ($C_{ss,av}$)
- maximum observed concentration at steady state ($C_{ss,max}$)
- minimum observed concentration at steady state ($C_{ss,min}$)
- peak–trough fluctuation (PTF)
- time at which the highest drug concentration occurs at steady state ($t_{ss,max}$)
- terminal elimination phase half-life ($t_{1/2}$)
- apparent total clearance following oral administration at steady state (CL_{ss}/F) (tazemetostat only)
- apparent volume of distribution at terminal phase (V_z/F) (tazemetostat only)
- accumulation ratio (R_{ac})

Urine PK parameters will be calculated using urine concentrations of tazemetostat are shown as below:

Cycle 0 Day 1 and Cycle 1 Day 15:

- amount of unchanged drug excreted in urine (A_e)
- fraction of dose excreted in urine (F_e)
- renal clearance (CL_R)

5.1.3 Exploratory Endpoints

CCI

5.2 Study Subjects

5.2.1 Definitions of Analysis Sets

DLT Analysis Set will include all subjects who have completed treatment Cycle 0 and 1 without major protocol deviations with at least 75% of treatment compliance in Cycle 1 and were assessed for DLT, and subjects who have experienced DLT during Cycle 0 and 1. Subjects with less than 75% treatment compliance in Cycle 1 due to a reason other than toxicity up to Cycle 1/Day 28 will not be included in this analysis set.

Safety/Efficacy Analysis Set will include all subjects who received at least 1 administration of the study drug. This will be the analysis set for all safety and efficacy evaluations, as well as for demographic and baseline characteristics.

Pharmacokinetic Analysis Set will include all subjects who have received at least 1 administration of the study drug and had sufficient PK data to derive at least 1 PK parameter.

5.2.2 Subject Disposition

Subjects who signed informed consent, were registered in the study, and failed screening and the reason for screen failures will be presented. Subjects who were treated, were not treated, were ongoing, and discontinued from study treatment and the reason for discontinuation will be presented.

5.2.3 Demographic and Other Baseline Characteristics

Demographic and other baseline characteristics for the Safety/Efficacy Analysis Set will be summarized in whole or each disease (DLBCL, follicular lymphoma (FL)). Continuous demographic and baseline variables include age, height, and body weight; categorical variables include sex, age group (<65, 65<=), race, ethnicity, ECOG-PS, Ann Arbor Staging at Screening, prior therapies for primary disease (chemotherapy, radiotherapy, Autologous Stem-Cell Transplantation and other therapies), B Symptoms and Disease diagnosis (DLBCL, FL).

MEDICAL HISTORY AND CURRENT MEDICAL CONDITION

A subject data listing of medical history and current medical conditions will be provided.

5.2.4 Prior and Concomitant Therapy

All investigator terms for medications recorded in the case report form (CRF) will be coded to an 11-digit code using the World Health Organization Drug Dictionary (WHO DD) preferred name. Prior medications will be defined as medications that stopped before the first dose of study drug. Concomitant medications will be defined as medications that started before the first dose of study drug and were continuing at the time of the first dose of study drug, or started

on or after the date of the first dose of study drug up to the final observation. All prior and concomitant medications will be presented in subject data listings.

5.2.5 Treatment Compliance

Not calculated.

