### 9.1.2 Dose-Limiting Toxicities (DLT)

The starting dose of tazemetostat is 800 mg as a single dose (Cycle 0) and 800 mg BID as continuous dosing (Cycle 1 and later). Three subjects will be enrolled and ensure that they are evaluable for dose-limiting toxicities (DLTs) at the end of Cycle 1 of the cohort. When a DLT is observed in 0 or 1 of 3 subjects at a given dose level, 3 additional subjects would be treated at the same dose level. When 2 of 3 subjects at a given dose level experience DLTs, enrollment of additional subjects will be discussed jointly by the investigator and sponsor.

The opinion of Independent Data Monitoring Advisor should be also obtained. When additional subjects are to be enrolled, they will be monitored individually. When no DLTs are observed, up to 3 additional subjects will be enrolled. When no additional subjects are accrued or 3 subjects in total experienced DLTs, the enrollment in the cohort will be discontinued and the lower dose level of tazemetostat cohort will be considered jointly by the investigator and sponsor. The opinion of Independent Data Monitoring Advisor can be obtained if needed.

If the subject is regarded as DLT non-evaluable (eg, early discontinuation due to non-DLT, medication compliance with <75% in Cycle 1 as a result of the reason other than treatment related toxicity), another subject will be added for replacement.

A DLT is defined as toxicity related to study drug in Table 1 below. The tolerability of tazemetostat will be determined based on the incidence of DLTs in Cycles 0 and 1. If DLTs occur in 0 or 1 of 6 subjects, this dose level is considered tolerable. If DLTs occurs in 2 of 6 subjects, the tolerability of this dose level will be determined jointly by the investigator and sponsor. The opinion of Independent Data Monitoring Advisor should be also obtained. In the case of difficulty of determination of whether a subject should be counted as having experienced a DLT and/or not for tolerability assessment, the final determination will be made jointly by the investigator and sponsor. The opinion of Independent Data Monitoring Advisor can be obtained if needed.

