**Table 1 Dose-Limiting Toxicities (DLT)**

Toxicity Category	Toxicity/CTCAE Grade
Hematological Toxicity	
 
• Grade 4 neutropenia for > 7 days or neutropenia requiring hematopoietic growth factors
 
• ≥ Grade 3 febrile neutropenia
 
• Grade 4 thrombocytopenia, Grade 3 thrombocytopenia with bleeding, or thrombocytopenia requiring platelet transfusion
 
• Grade 4 anemia or anemia requiring erythrocyte transfusion
 

Non-hematological Toxicity	
 
• ≥ Grade 3 nausea, vomiting, or diarrhea that persists > 7 days despite maximal medical therapy
 
• ≥ Grade 3 non-hematological laboratory abnormalities with clinical symptoms that persists > 7 days
 
• Other Grade 3 toxicity lasting > 7 days or Grade 4 non-hematological toxicity of any duration
 

Medication compliance	
 
• Failure to administer ≥ 75% (≥ 42/56 doses) of the planned administration number of study drug in Cycle 1 as a result of treatment-related toxicity
 

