#### **No DLT:**

Tazemetostat administration will be interrupted if judged to be clinically needed by investigator or subinvestigator, and may be resumed at the same dose level at appropriate timing.

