The starting dose of tazemetostat is 800 mg as a single dose (Cycle 0) and 800 mg BID as continuous dosing (Cycle 1 and later). Three subjects will be enrolled and ensure that 3 subjects are evaluable for dose-limiting toxicities (DLTs) at the end of Cycle 1 of the cohort. When a DLT is observed in 0 or 1 of 3 subjects at a given dose level, 3 additional subjects would be treated at the same dose level. When 2 of 3 subjects at a given dose level experience DLTs, enrollment of additional subjects will be discussed jointly by the investigator and sponsor. The opinion of Independent Data Monitoring Advisor should be also obtained. When additional subjects are to be enrolled, they will be monitored individually. When no DLTs are observed, up to 3 additional subjects will be enrolled. When no additional subjects are accrued or 3 subjects in total experienced DLTs, the enrollment in the cohort will be discontinued and the lower dose level of tazemetostat cohort will be considered jointly by the investigator and sponsor. The opinion of Independent Data Monitoring Advisor can be obtained, if needed.

If the subject is regarded as DLT non-evaluable (eg, early discontinuation due to non-DLT, medication compliance with < 75% in Cycle 1 as a result of the reason other than treatment related toxicity), another subject will be added for replacement.

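### Does the SAP need a compliance calculation and a mixed-cause rule to class a subject who falls below 42 of 56 Cycle 1 doses?

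*SAP*

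**What the plan says.** SAP 5.2.5 consists of two words: "Not calculated". Compliance nevertheless enters the primary endpoint in three places.

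- **Protocol Table 1** lists as a DLT the failure to take at least 75% (42/56) "of the planned administration number of study drug in Cycle 1 as a result of treatment-related toxicity".
- **SAP 3.2 and Protocol 9.1.2** treat a subject below 75% "in Cycle 1 as a result of the reason other than treatment related toxicity" as non-evaluable and add a replacement.
- **SAP 5.2.1** admits subjects who completed Cycles 0 and 1 with at least 75% compliance and were assessed for DLT, and also subjects who had a DLT. It adds that those below 75% "due to a reason other than toxicity up to Cycle 1/Day 28 will not be included in this analysis set".

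Protocol 9.4.1.1.1 says that, absent a DLT, "Tazemetostat administration will be interrupted if judged to be clinically needed by investigator or subinvestigator". One subject can therefore miss some doses for drug toxicity and others for unrelated reasons.

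Protocol 9.1.2 also has a clause for doubtful cases. It begins "In the case of difficulty of determination of whether a subject should be counted as having experienced a DLT" and assigns the final decision to the investigator and sponsor jointly; "The opinion of Independent Data Monitoring Advisor can be obtained if needed".

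**The concern.** The SAP appears to decline to compute a quantity that its own primary analysis set needs. The DLT and replacement rules also each assume a single cause. If 1 to 14 doses are missed for each cause and 15 or more in total, the subject is below the cut-off although neither cause alone would put them there. If a contributing cause is enough, the DLT rule and the exclusion both apply. If a sole cause is required, neither does.

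The stake is the count out of six. Protocol 9.1.2 says "If DLTs occur in 0 or 1 of 6 subjects, this dose level is considered tolerable", whereas 2 of 6 goes to a joint decision for which the Independent Data Monitoring Advisor's opinion is expected. With one other DLT in the cohort, counting the mixed-cause subject gives 2 of 6. Replacing that subject with one who has no DLT gives 1 of 6. The classification is made open-label, and the Advisor's view on it is optional.

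**Working it through.** **The cut-off.** 28 days × 2 doses = 56, and 0.75 × 56 = 42, which reproduces Table 1. Fourteen missed doses leave 42/56 = 75.0% (passes); fifteen leave 41/56 = 73.2% (fails).

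**The ambiguous region.** Let T be doses missed for treatment-related toxicity and O doses missed for other reasons. The region is 1 ≤ T ≤ 14, 1 ≤ O ≤ 14, T + O ≥ 15, so totals run from 15 to 28. With T = O = 8, the subject took 40/56 = 71.4%; either cause alone leaves 48/56 = 85.7%.

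**Set membership.** SAP 5.2.1 has two ways in: at least 75% compliance with DLT assessment, or a DLT. A subject in this region fails the first, so membership depends only on whether the subject is a DLT.

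- Not a DLT: the subject is outside the set and non-evaluable. The non-evaluable cases in Protocol 9.1.2 are given as examples, so replacement follows.
- A DLT: the second way in applies. The exclusion sentence is sensibly read as describing subjects below 75% who are not DLTs.

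The only open question is what the causal phrase in Table 1 covers. That is a question of DLT status, which the doubtful-case clause assigns.

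**Data.** Protocol 9.4.9 puts administration dates and doses on the CRF. Protocol 11.5 names reasons for dose modification and the relationship of each AE to study drug. SAP 5.6.3 lists AEs leading to interruption. Doses taken out of 56 can be counted from these; a reason for every single missed dose is not expressly named.

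**Effect of one such subject.** For an assumed DLT rate p in the other subjects, replacement gives P(outright tolerable) = P(X ≤ 1 of 6), and counting gives P(0 of the other 5) = (1 − p)^5.

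| p (assumed) | Replaced | Counted |
|---|---|---|
| 5% | 96.7% | 77.4% |
| 10% | 88.6% | 59.0% |
| 20% | 65.5% | 32.8% |

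**Effect before knowing whether one occurs.** Let q be the per-subject chance of a mixed-cause case and p that of a clear DLT, both assumed. Counting gives Binomial(6, p + q); replacement gives Binomial(6, p/(1 − q)). At p = 10%, q = 5%:

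- Counted: 0.85^6 + 6 × 0.15 × 0.85^5 = 0.377 + 0.399 = 77.6%.
- Replaced: p/(1 − q) = 0.1053, giving 0.513 + 0.362 = 87.5%.

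The gap is 9.9 points. It is 2.7 points at p = 5%, q = 2% (93.9% against 96.6%) and 20.8 points at p = q = 10% (65.5% against 86.3%). The chance of at least one such subject in six is 1 − (1 − q)^6, which is 11.4% at q = 2% and 46.9% at q = 10%.

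**When the branch moves.** With no other DLT the result is 0 or 1 of 6, tolerable either way. With exactly one other, it is 1 or 2 of 6. With two others, it is 2 or 3 of 6, so the choice lies between joint decision and cohort closure; neither is outright tolerable. These counts assume the replacement has no DLT.

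**The case for a change.** The strongest case for a change is that the doubtful-case clause names who decides but not by what criterion. In a six-subject open-label cohort, the people classing the subject may already know the other outcomes, and their choice can settle whether the Advisor must be consulted on tolerability. SAP 3.2 does not repeat the clause, and SAP 5.6.2 tabulates DLTs by preferred term, which would not show that a DLT arose from missed doses. Two SAP sentences, one protocol sentence and a listing column look cheap.

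Part of this stands: no attribution criterion is written down, and the report would be easier to follow if it named the Table 1 criterion met. The rest carries less weight.

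- SAP 3.2 omits the whole tolerability rule and the DLT table as well as this clause. It is a summary, and the protocol governs.
- Cohort decisions follow Protocol 9.1.2 during the study, while Protocol 9.7 places the statistical analyses after lock. Editing SAP 5.2.5 would not alter a cohort decision.
- The first three subjects are assessed before the next three are treated, so not every classification is made with all other outcomes known.
- The suggested remedy asks for some rule without giving grounds for preferring one. It would replace case judgement with an arbitrary convention, and changing how DLTs are counted would need a protocol amendment.

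The wording also varies. SAP 5.2.1 and Protocol 9.7.1.2 refer to toxicity, whereas Table 1, Protocol 9.1.2 and SAP 3.2 specify treatment-related toxicity. This is loose drafting without effect on membership, because a subject below 75% enters the set only as a DLT.

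**Conclusion.** No change to the plan follows. SAP 5.2.5 sits among disposition, baseline and concomitant-therapy reporting and is most naturally read as saying that no compliance summary will be produced. An analyst can still count Cycle 1 doses against 42/56 and apply the recorded DLT determination. The mixed-cause case is a missing detail with a named decision process, and the plan followed as written still classes the subject.

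The effect could be material if the case arose: about 30 points in the chance of an outright tolerable result at an assumed 10% DLT rate (88.6% − 59.0% = 29.6). Even then, 2 of 6 leads to a joint decision that may still find the dose tolerable. The case needs at least 15 missed doses from two causes, at most 14 from each, and no other DLT in that subject.

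The documents give no frequency, and the 2–10% range for q is an assumption without a source. What they do report points towards rarity. Protocol 7.3.3 records one DLT, at 1600 mg BID, and 5 of 89 subjects discontinuing for AEs. Subjects are also in hospital from C0D1 to C1D15, which covers the first 14 days of Cycle 1, or 28 of its 56 doses. This conclusion rests on reading 5.2.5 as a reporting statement; the separate programming specifications and table shells (SAP 9 and 11) were not available to confirm it.

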5.3 Data Analysis General Considerations

All efficacy analyses will be conducted based on Efficacy Analysis Set.

5.3.1 Pooling of Centers

Subjects from all centers will be pooled for all analyses.

5.3.2 Adjustments for Covariates

No adjustment for covariates will be performed.

5.3.3 Multiple Comparisons/Multiplicity

No statistical comparison is planned in this study.

5.3.4 Examination of Subgroups

All efficacy analyses will be conducted in whole or each disease (DLBCL, FL).

5.3.5 Handling of Missing Data, Dropouts, and Outliers

No imputation will be performed for missing data.

Data exceptions will be identified before data base lock based on discussion with medical experts if necessary.

5.4 Efficacy Analyses

BOR will be summarized in whole or each disease (DLBCL, FL). The assessment of the ORR (complete response (CR) + partial response (PR)) in subjects with B cell lymphomas will be based on “The Lugano Classification (CT-Based Response)” (Cheson, et al., 2014) response criteria.

ORR will be presented with corresponding 2-sided Clopper–Pearson exact 95% confidence intervals (CIs). This analysis will be performed on the Efficacy Analysis Set. If applicable, a waterfall plot will be presented for the percent changes from baseline in the sum of the diameters of target lesions at post-baseline nadir.

5.5 Pharmacokinetic, Pharmacodynamic, Pharmacogenomic, and Other Biomarker Analyses

5.5.1 Pharmacokinetic Analyses

The Safety Analysis Set will be used for individual listings of tazemetostat and its metabolite (ER-897387) plasma concentrations and urine tazemetostat concentrations. The PK Analysis Set will be used for the summaries of tazemetostat and ER-897387 plasma concentrations and urine tazemetostat concentrations and for summaries and listings of PK parameters. When necessary, molecular weight (free base) 572.74 for the parent and 544.68 for ER-897387 will be used. The data in patient with dose-reduction/interruption will not be included on calculation of summary statistics.

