#### **If DLT occurs:**

Tazemetostat administration should be interrupted immediately. Treatment may be resumed in Cycle 2 at 600 mg BID (1200 mg total daily dose) if toxicity is resolved to Grade  $\leq 1$  or baseline and the investigator or subinvestigator decides to continue the study.

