**Table 6 Schedule of Procedures/Assessments in Study E7438-J081-106 (EZH-106)**

Phase	Pre-treatment		Treatment						Extension		Follow-up	
Period	Screening a	Baseline	Cycle 0	Cycle 1					Cycle 2 and later		Discontinuation	Final observation
Day	Within 28 days before administration	Within 3 days before administration	1	1 b	3	8 (±1)	15 (±1)	22 (±1)	1 (±3) c	15 (±3) n	(+7)	30 days after last dosing (+7) d
Informed Consent	X								[X] m			
Demographic data	X											
Inclusion/exclusion Criteria	X	X										
Medical history/Current medical condition	X											
Previous therapy	X											
Height	X											
Body weight	X	X		X		X	X	X	X	X	X	
Physical examination	X	X	X	X		X	X	X	X	X	X	X
Vital signs	X		X	X		X	X	X	X	X	X	X
ECOG-PS	X	X		X					X		X	
12-lead ECGs e	X		X	X			X		X	X	X	
Echocardiogram or MUGA scan f	X								[X]			
Pregnancy test (if applicable)	X										X	
Virus test	X											
Hematology o	X	X		X		X	X	X	X	X	X	X
Blood chemistry	X	X		X		X	X	X	X	X	X	X
Urinalysis	X	X		X		X	X	X	X	X	X	X
PK (blood) g			X		X	X	X	X	[X]			
PK (urine) h			X				X					
Tumor assessments (CT) i	X									[X]	X	
Bone marrow aspiration or biopsy j	X									[X]		
Tazemetostat administration k			X	Continuous 28-day cycle of tazemetostat twice daily.								
Archival tumor sample submission l				X								
Adverse events				From informed consent to final observation								

Concomitant drug/therapies	From informed consent to final observation
----------------------------	--

Note, [X]: In case to perform.

C#/D# = Cycle #/Day #, CR = complete response, CT = computed tomography, ECG = electrocardiogram, ECOG-PS = Eastern Cooperative Oncology Group-Performance Status, MUGA = multigated acquisition, PK = pharmacokinetics.

a: Screening assessments may be used as baseline assessments if performed within 3 days of the first administration of study drug.

b: To start C1D1 on Cycle 0 Days 4-9.

c: +1 day for C2D1.

d: When subject needs to receive other anti-tumor therapy due to deterioration of the disease within 30 days after the final study drug administration, final observation must be conducted before initiation of other anti-tumor therapy and the data within 7 days before next anti-tumor therapy can be used for final observation. .

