e: 12-Lead ECGs on C0D1, C1D1, and C2D1 will be collected at pre-dose and 0.5-2 hours post dose of first administration.

f: Echocardiogram or MUGA scan will be performed at screening, every 16 weeks (ie, Day 1 of every 4 cycles [ $\pm$  1 week]) from C2D1. Additional assessments may be performed if clinically indicated.

g: Blood samples for PK analyses of tazemetostat and metabolites will be collected in C0D1 at predose, 0.5, 1, 2, 4, 6, 8, 10, 12, 24, 48 and 72 hours postdose; C1D3 and C1D8 at predose of first administration; C1D15 at predose of first administration, 0.5, 1, 2, 4, 6, 8, 10, and 12 hours postdose (postdose blood samples should be collected before the second administration of study drug); C1D22 and C2D1 predose of first administration.

h: Urine samples for PK analyses of tazemetostat will be collected in C0D1 at predose, 0-24, 24-48 and 48-72 hours postdose; C1D15 at 0-12 hours postdose of first administration.

i: The data of tumor assessments before informed consent within 28 days from study drug administration can be used as screening data if it meets the requirement of the protocol. Perform tumor assessment at screening, every 8 weeks [ $\pm$ 1 week] (starting at Cycle 1 Day 1) during Cycles 2-6, every 12 weeks [ $\pm$  1 week] starting at Cycle 7 and beyond, and discontinuation. The data within 28 days can be used as discontinuation data.

j: The data of bone marrow aspiration or biopsy before informed consent within 42 days from study drug administration can be used as screening data if it meets the requirement of the protocol. After the study drug dosing, perform bone marrow aspiration or biopsy if the result of screening was positive or unconfirmed and when to confirm CR as best of response or if clinically indicated.

k: Subjects should not take study drug before evaluations are performed (except tumor assessments and peripheral blood smear morphology assessment), unless specified.

l: Submit pre-study drug treated tumor sample to central laboratory before final observation, as far as possible.

m: Informed consent should be obtained before initiating the study or before entering the Extension Phase when Cycle 2 or later administrations will be continued.

n: In Cycle 13 or later, visits and assessments on Day 15 can be omitted at the discretion of the investigator or subinvestigator, if there was no concern for safety of the subject.

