#### 9.7.1.7 Pharmacokinetic, Pharmacodynamic, Pharmacogenomic, and Other Biomarker Analyses

##### 9.7.1.7.1 PHARMACOKINETIC ANALYSES

The PK Analysis Set will be used for all PK analyses including summaries of plasma and urine concentrations of tazemetostat and plasma concentrations of ER-897387. Plasma concentration-time profiles of tazemetostat and ER-897387 will be plotted. Using non-compartmental analysis methods, plasma concentrations of tazemetostat and ER-897387 will be calculated to determine the PK parameters including  $C_{max}$ ,  $t_{max}$ , AUC at the first administration (Cycle 0/Day 1) and repeated administration (Cycle 1/Day 15).

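### SAP 5.5.1 drops every PK value of a patient with any dose reduction or interruption from the summary statistics, although 12 to 25 of the 25 planned plasma samples come before the first withheld dose

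*SAP*

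**What the plan says.** SAP 5.5.1 assigns summaries of concentrations and PK parameters to the PK Analysis Set, and then adds: "The data in patient with dose-reduction/interruption will not be included on calculation of summary statistics." It gives no time, cycle, profile, cause or duration. SAP 5.3.5 (missing data and outliers), 5.5.1.1 and 5.5.1.2 (plasma and urine analyses), 7 (data handling) and 8.1.2 (anomalous concentrations) add no limit.

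Protocol 9.7.1.7.1 has no such exclusion: "The PK Analysis Set will be used for all PK analyses including summaries of plasma and urine concentrations of tazemetostat". The PK Analysis Set needs only one dose and one derivable parameter. SAP section 8, which lists departures from the protocol's planned analyses, does not mention the exclusion.

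The sampling schedule is in Protocol Tables 3 and 4 and the Table 6 footnotes:

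- Cycle 0 plasma is "collected in C0D1 at predose, 0.5, 1, 2, 4, 6, 8, 10, 12, 24, 48 and 72 hours postdose".
- The last plasma samples are "C1D22 and C2D1 predose of first administration".
- For urine: "Urine samples for PK analyses of tazemetostat will be collected in C0D1 at predose, 0-24, 24-48 and 48-72 hours postdose", plus one 0–12 h collection on C1D15.
- Cycle 1 timing is "To start C1D1 on Cycle 0 Days 4-9", and on visit days "Subjects should not take study drug before evaluations are performed", with stated exceptions that do not include PK sampling.

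**The concern.** An exclusion for dose changes is reasonable for samples that the change could have altered. This one is attached to the patient, so it also removes samples that could not have been altered. Four features of the design show this.

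1. Cycle 0 is one dose, followed for 72 hours. No further dose is due until C1D1, so no withheld dose can change that profile.
2. The protocol sets out dose reductions only from Cycle 2, and PK sampling ends with the C2D1 predose sample. For reductions, the rule can therefore only remove samples taken at the assigned dose.
3. An interruption that starts after the C1D15 profile cannot change that profile.
4. Treatment is open-ended, and Protocol 9.4.1.1.2 allows interruption for events unrelated to the drug. An interruption many cycles after the last PK sample would still trigger the exclusion.

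PK is a secondary objective, the protocol states that no Japanese clinical data exist, and the plan is for six evaluable subjects. Replacement does not restore the loss, because Protocol 9.1.2 replaces only subjects who are not evaluable for DLT. Three kinds of subject stay evaluable yet lose all their PK summary data: one with a DLT, one who misses up to 14 Cycle 1 doses for reasons other than toxicity, and one first interrupted in Cycle 2 or later. For a DLT in Cycle 0 or 1 the protocol says "Tazemetostat administration should be interrupted immediately". Such subjects count towards tolerability but would be missing from the single-dose exposure summary.

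**Working it through.** The documents state no total sample count, so there is no plan figure to reproduce. The counts below come from Protocol Table 3 and agree with Table 6 footnote g.

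**Planned plasma samples per subject.** C0D1 12 + C1D3 1 + C1D8 1 + C1D15 9 (predose and eight postdose) + C1D22 1 + C2D1 1 = 25.

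**Samples before the event.** The event is dated from the first planned dose withheld. The share is the cumulative sample count divided by 25.

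| First withheld dose | Samples already taken | Share | Kept in summaries under SAP 5.5.1 as worded |
|---|---|---|---|
| C1D1 to before the C1D3 sample | 12 | 12/25 = 48% | 0 |
| Between C1D3 and C1D8 | 13 | 13/25 = 52% | 0 |
| Between C1D8 and C1D15 | 14 | 14/25 = 56% | 0 |
| Between the C1D15 profile and C1D22 | 23 | 23/25 = 92% | 0 |
| Between C1D22 and C2D1 | 24 | 24/25 = 96% | 0 |
| Cycle 2 or later | 25 | 25/25 = 100% | 0 |

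The lower bound is 12 because C1D1 can start no earlier than Cycle 0 Day 4, the day of the 72 h sample, and that day's evaluations come before dosing.

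**Reductions.** A subject with a DLT in Cycle 0 or 1 may resume at a lower dose only in Cycle 2 (Protocol 9.4.1.1.1). The other reductions fall under the rules for Cycle 2 and later (9.4.1.1.2). The last sample is taken before the first Cycle 2 dose, so 25 of 25 precede any protocol reduction.

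**Urine.** Three of the four postdose collections (0–24, 24–48 and 48–72 h) belong to the Cycle 0 dose.

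**Summaries affected at C0D1 (SAP 5.5.1.1).**

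- Concentrations: 12 time points × 2 analytes = 24.
- Parameters: Cmax, tmax, three AUCs, λz, t1/2 and MRT make 8; 8 × 2 analytes = 16. Adding two metabolite-to-parent ratios, CL/F and Vz/F gives 16 + 2 + 2 = 20.

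**Effect on n.** With six subjects, one exclusion leaves 5, a loss of (6 − 5)/6 = 17%. Two leave 4 (33%) and three leave 3 (50%).

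**Missed doses without replacement.** The Cycle 1 compliance threshold is 42 of 56 doses, so 56 − 42 = 14 doses (14/56 = 25%) can be missed with the subject still evaluable.

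**The case against.** The strongest reply is that the sentence is loosely written and means data obtained under a reduction or interruption, since the literal reading gives an absurd result: a Cycle 10 interruption erasing the Cycle 0 profile. That intention is plausible. It is also true that reduction and interruption are a stock pairing in these documents, so the fact that the reduction term would then have nothing to act on is only weak evidence of what was meant. But the sentence names the patient, and two programmers could produce different tables from it. The non-compartmental analysis manual is not available to read. The SAP cites it for parameter derivation, values below quantification and anomalous concentrations, not for this rule. Leaving the matter to a decision before database lock, in an open-label study, is a poor substitute for a stated rule.

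Several limits stand:

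- If an interruption is ordered during Cycle 0 itself, fewer than 12 samples may precede the order in clock time. Dating from the first withheld dose removes the difficulty, and the Cycle 0 profile is unaffected either way.
- The 24 and 20 summaries all reflect one fact, that n falls by one. Two of the 24 are predose time points.
- The 17% assumes exactly six subjects. Replacements could make the PK Analysis Set larger; with seven the loss is 1/7 = 14%.
- The analyses are descriptive, and individual values remain listed and plotted, so a reader could rebuild the summaries.
- The protocol leaves analysis detail to the SAP, so omission from section 8 is a secondary point.

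**Conclusion.** The concern holds. As worded, the rule removes all 25 planned plasma samples of an affected patient from the summary statistics, when 12 (48%) to 25 (100%) of them precede the first withheld dose and all 25 precede any protocol reduction. With six subjects, each such patient costs one sixth of the n in every Cycle 0 summary. The conclusion rests on the literal wording, on dating the event from the first withheld dose, and on a PK Analysis Set of six. The documents give neither an interruption rate nor a relation between interruption and exposure, so the chance of this happening and any resulting bias cannot be stated. The primary endpoint is not affected. The wording should be corrected before the summaries are produced.

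**What to change.** Replace the sentence in SAP 5.5.1 with a rule tied to the sample:

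> C0D1 plasma and urine data are summarised for all subjects in the PK Analysis Set. A Cycle 1 or C2D1 trough, or the C1D15 profile with its urine collection and derived parameters (including Rac and Rss), is excluded from summary statistics only if a dose interruption, or a reduction from the assigned dose, began before that sample or profile. An interruption is dated from the first withheld dose. Later reductions or interruptions do not lead to exclusion.

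List each exclusion with its reason, and record the rule in SAP section 8 as a narrowing of Protocol 9.7.1.7.1.

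The cost is this wording and one flag variable. Dosing dates and doses (Protocol 9.4.9) and PK sampling times (9.5.1.4.1) are already on the CRF, so no new data and no extra table are needed. The rule is deliberately conservative: even a brief early Cycle 1 interruption would remove that subject's C1D15 profile from the summaries. It removes nothing that the present sentence, read literally, would keep. If the sponsor prefers a shorter look-back for steady state, it can define one, provided this is done before database lock.
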